There is evidence that males may be at risk of decreased spermatogenesis following PRRT with ¹⁷⁷Lu-dotatate. In a study by (Teunissen, et al., 2009), a significant decrease of mean serum inhibin B levels was observed in male patients (N=35) treated with ¹⁷⁷Lu-dotatate. It has been demonstrated that serum inhibin B levels are positively correlated with spermatogenic status and sperm count (Pierik, Vreeburg, Stijnen, De Jong, & Weber, 1998). The study (Teunissen, et al., 2009) also found recovery to almost pretreatment levels after 24 months. The potential long-term genetic damage to spermatogenic cells has not been studied.

Women and men should not procreate until six months after the end of their last treatment with Lutathera. However, due to additional exposure from CT scans taken during the study, women in both arms should also not procreate during the whole treatment period of the study. Women of child bearing potential and sexually active males must be informed that taking the study treatment may involve unknown risks to the fetus if pregnancy were to occur during the study, and agree that in order to participate in the study they must adhere to the contraception requirements outlined in the exclusion criteria and in Appendix 1. If there is any question that the subject will not reliably comply, they should not be entered or continue in the study.

Based on the FDA guidance for inclusion of adolescents in the adult oncology trials and the consensus expert opinion presented by the European multi-stakeholder platform ACCELERATE it is recommended that adolescents can receive the same dose administered in adults if there is no relevant effect of body size on pharmacokinetics, which is the case for both, Lutathera and octreotide long-acting. Based on the similar clinical presentation of the disease under evaluation in adolescents, the following inclusion criteria have been chosen for this study: ≥ 15 years old and >40 kg BW (aligned with the BW recommendation from the FDA guidance).

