5.2 Exclusion criteria

Subjects meeting any of the following criteria are not eligible for inclusion in this study.

- 1. Creatinine clearance <40 mL/min calculated by the Cockroft Gault method.
- 2. Hb concentration <5.0 mmol/L (<8.0 g/dL); WBC <2x10⁹/L (2000/mm³); platelets <75x10⁹/L (75x10³/mm³).
- 3. Total bilirubin >3 x ULN.
- 4. Serum albumin <3.0 g/dL unless prothrombin time is within the normal range.
- 5. Pregnancy or lactation.

6. A) Women of child-bearing potential, defined as all women physiologically capable of becoming pregnant, are not allowed to participate in this study UNLESS they are using highly effective methods of contraception throughout the study treatment period (including cross-over and re-treatment, if applicable) and for 7 months after study drug discontinuation. Highly effective contraception methods include:

• True abstinence when this is in line with the preferred and usual lifestyle of the patient. Periodic abstinence (e.g., calendar, ovulation, symptothermal, post-ovulation methods), declaration of abstinence for the duration of exposure to IMP, and withdrawal are not acceptable methods of contraception.

- Male or female sterilization
- Combination of any two of the following (a+b or a+c or b+c):

a. Use of oral, injected, or implanted hormonal methods of contraception. In case of use of oral contraception, women should be stable on the same pill for a minimum of 3 months before taking study treatment.

b. Placement of an intrauterine device (IUD) or intrauterine system (IUS)

c. Barrier methods of contraception: condom or occlusive cap (diaphragm or cervical/vault caps) with spermicidal foam/gel/film/cream/vaginal suppository. Post-menopausal women are allowed to participate in this study. Women are considered post-menopausal and not of child bearing potential if they have had 12 months of natural (spontaneous) amenorrhea with an appropriate clinical profile (e.g. age appropriate, history of vasomotor symptoms) confirmed by a high follicle stimulating hormone (FSH) level, or have had surgical bilateral oophorectomy (with or without hysterectomy) or tubal ligation at least six weeks prior to screening. In the case of oophorectomy alone, only when the reproductive status of the woman has been confirmed by follow up hormone level assessment is she considered not of child bearing potential.

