Informed consent must be obtained before conducting any study-specific procedures (e.g. all of the procedures described in the protocol). The process of obtaining informed consent must be documented in the subject source documents.

Advanced Accelerator Applications will provide to investigators in a separate document a proposed informed consent form that complies with the ICH GCP guidelines and regulatory requirements and is considered appropriate for this study. Any changes to the proposed consent form suggested by the investigator must be agreed by Advanced Accelerator Applications before submission to the IRB/IEC.

Information about common side effects already known about the investigational drug can be found in the IB. This information will be included in the subject informed consent and should be discussed with the subject during the study as needed. Any new information regarding the safety profile of the investigational drug that is identified between IB updates will be communicated as appropriate, for example, via an investigator notification or an aggregate safety finding. New information might require an update to the informed consent and then must be discussed with the subject.

Women of child bearing potential must be informed that taking Lutathera can cause fetal harm when administered to a pregnant woman and agree that in order to participate in the study they must adhere to the contraception requirements. Male subjects must be informed that if a female partner becomes pregnant while he is enrolled in the study, contact with the female partner will be attempted to request her consent to collect pregnancy outcome information. Subjects must be informed of the contraception requirements outlined in the Inclusion/Exclusion Criteria (Section 5).

A copy of the approved version of all consent forms must be provided to Advanced Accelerator Applications after IRB/IEC approval.

It is recommended that the Investigator inform the patient's general practitioner of his/her participation in the study, provided that the patient has a general practitioner and the patient agrees to disclose this information.

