Est. Creatinine Clearance = [[140 - age (yr)]^*weight (kg)]/[72^*serum Cr(mg/dL)] (multiply by 0.85 for women)
Or
```

*Est. Creatinine Clearance = [[140-age(yr)]*weight (kg)]/[0.814* serum Cr(umol/L)]* (multiply by 0.85 for women)

⁴ In South Korea only, CgA assessment being discontinued in Q3 2022 due to lab kits shortage

⁵ For UK, serum pregnancy test is mandatory at baseline

During the Follow-up Phase, in both study arms laboratory assessments (hematology and blood chemistry) will be performed every 6 months (± 1 month).

8.5.3 **Pregnancy Test**

Women who receive Lutathera in the study, including those who crossed over to Lutathera and those re-treated with Lutathera, should not procreate during Lutathera treatment and until six months after the end of their last treatment with Lutathera, or until the end of treatment period of the study, whichever is longer. Women in the control arm should not procreate until the end of treatment period.

A pregnancy test (either on urine or blood) must be performed at baseline and within 14 days (preferably 7 days) prior to each Lutathera treatment for every female patient of childbearing potential (Section 5 and Appendix 1).

Ionizing radiations of lutetium (177Lu) oxodotreotide may potentially have temporary toxic effects on female and male gonads (decrease of inhibin-B and concomitant increase of FSH, suggesting radiation damage to Sertoli cells). Fertility is usually restored 12 to 18 months after treatment. The participant will be recommended to seek genetic consultation before starting treatment if the patient wishes to have children after treatment, which includes the option of cryopreservation of sperm or eggs before treatment starts.

For UK only:

A pregnancy test (blood) must be performed at baseline in both arms and within 7 days prior to the first Lutathera treatment. A urine or blood pregnancy test must be performed within 7 days prior to each Lutathera treatment for every female patient of childbearing potential (Section 5 and Appendix 1). A urine or blood pregnancy test must be performed in both arms at the end of the relevant systemic exposure to octreotide.

For Germany only:

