Appendix 1 – Precautions for Pregnancy

Women who receive Lutathera, including those in cross-over arm and those who are re-treated with Lutathera, should not procreate until seven months after the date of their last treatment with ¹⁷⁷Lu-DOTA⁰- Tyr³-Octreotate, or until the end of treatment period of the study (due to the CT scans foreseen during the study (every 12 ± 1 weeks)), whichever is longer. Women in the control arm should not procreate until the end of treatment period.

It is noteworthy that β -HCG may be secreted by a small percentage of NETs, such that, in addition to being a pregnancy marker it also is a tumor marker. Consequently, NET female patients with positive β -HCG at baseline can be eligible to enter the study and receive treatment if pregnancy can be excluded by lack of expected doubling of β -HCG. Normally in pregnant subjects β -HCG doubles every 2 days during the first 4 weeks of pregnancy and every 3 $\frac{1}{2}$ days by weeks 6 to 7.

Women of childbearing potential include any female who has experienced menarche and who has not undergone successful surgical sterilisation (hysterectomy, bilateral tubal ligation or bilateral ovariectomy) or is not postmenopausal (defined as amenorrhoea >12 consecutive months, and for women on hormone replacement therapy, only with a documented plasma follicle-stimulating hormone level >35 mIU/mL). Even women who are using oral, implanted or injected contraceptive hormones, an IUD, or barrier methods (diaphragm, condoms, spermicidal) to prevent pregnancy, are practicing true abstinence (see definition below) or where the partner is sterile (e.g. vasectomy, see below) should be considered to be of childbearing potential.

Highly effective methods of contraception must be used throughout the study and for 6 months after study drug discontinuation. Highly effective contraception methods include:

• True abstinence must be in line with the preferred and usual lifestyle of the patient. Periodic abstinence (e.g., calendar, ovulation, symptothermal, post-ovulation methods), declaration of abstinence for the duration of exposure to IMP, and withdrawal are not acceptable methods of contraception.

• Male or female sterilization (vasectomized partner is a highly effective birth control method provided that partner is the sole sexual partner of the trial participant and that the vasectomized partner has received medical assessment of the surgical success).

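### Protocol Section 8.5.3 still gives women six months after the last Lutathera treatment, where the opening of Appendix 1 gives the same women seven; Section 4.5 and a later Appendix 1 sentence also keep six.

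*Protocol*

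**What the plan says.** Four places in the protocol, beside the eligibility rule, set how long women must avoid pregnancy.

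- **Section 8.5.3 (Pregnancy Test).** Women who receive Lutathera, expressly including those crossed over or re-treated, should not procreate "until six months after the end of their last treatment with Lutathera, or until the end of treatment period of the study", taking the longer.
- **Appendix 1, opening paragraph.** The same women "should not procreate until seven months after the date of their last treatment with" Lutathera, or until the treatment period ends, again taking the longer.
- **Section 4.5 (Risks and benefits).** "Women and men should not procreate until six months after the end of their last treatment with Lutathera". The next sentence adds that women in both arms should not procreate during the whole treatment period, because of the CT scans.
- **Appendix 1, later sentence.** Highly effective contraception is required during the study and for 6 months counted from study drug discontinuation.

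Exclusion criterion 6A (Section 5.2, repeated in the synopsis) requires highly effective contraception during treatment "and for 7 months after study drug discontinuation". The Amendment 2.0 rationale explains that figure. The guideline formula gives 6 months and 10 days after the last dose, and the sponsor extended the period from 6 to 7 months as a precaution. For men, criterion 6B and Appendix 1 set four months.

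**The concern.** Section 8.5.3 and the Appendix 1 opening address the same women and start from the same event. Section 8.5.3 speaks of the end of the last treatment and Appendix 1 of its date, which for a 30-minute infusion is the same day. Both carry the same alternative end point, "or until the end of treatment period of the study, whichever is longer". Only the number differs, so both cannot be right. Both are current text, so this is not a difference between an amendment log and the protocol.

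The subject is fetal exposure after a radioligand. A site that took the period from Section 8.5.3 could tell a woman that she may conceive earlier than the sponsor intends. The instruction is still in use. Randomization is complete, but cross-over and re-treatment may begin up to four years after the last patient was randomized (Sections 3.3 and 3.4).

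**Working it through.** **Inputs.** Effective half-life 49 hours, and a formula of five half-lives plus 6 months (Amendment 2.0 rationale). Month = 30.4375 days (SAP 2.1.1.7). Fourth Lutathera dose at Week 24 on the ideal schedule (Tables 8-3 and 8-4). Cross-over end-of-treatment visit at Week 28 (Section 3.3).

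**The sponsor's own figure.** 5 × 49 h = 245 h; 245 / 24 = 10.2 days. Adding 6 months gives 6 months and 10 days, as stated.

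**The three periods, counted from the last Lutathera dose.**

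| Period | Days | Weeks | Ends, if dose 4 is at Week 24 |
|---|---|---|---|
| Six months (Section 8.5.3) | 6 × 30.4375 = 182.6 | 26.1 | Week 50.1 |
| Calculated period | 182.6 + 10.2 = 192.8 | 27.5 | Week 51.5 |
| Seven months (Appendix 1 opening) | 7 × 30.4375 = 213.1 | 30.4 | Week 54.4 |

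Six months is 10.2 days short of the calculated period and 30.4 days short of the seven-month rule.

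**When the difference takes effect.** Let the treatment period end at week T. Section 8.5.3 releases the woman at the later of T and Week 50.1; the Appendix 1 opening releases her at the later of T and Week 54.4.

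- T at or before Week 50.1: the full 30.4 days.
- T between Weeks 50.1 and 54.4: the part that remains, 54.4 − T weeks.
- T after Week 54.4: none. This covers a woman who stays on octreotide without progression to Week 72.

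Early ends of treatment are foreseen. In cross-over, the end-of-treatment visit is 28 − 24 = 4 weeks after the fourth dose, well inside 26.1 weeks, so the month count decides. The same holds for a Lutathera-arm woman whose treatment period ends early through progression.

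**The later Appendix 1 sentence.** It starts from study drug discontinuation, so the week figures above do not apply to it. The proper comparison is criterion 6A, which uses that same start and says 7 months. The mismatch is 6 against 7 on one clock.

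**Section 4.5.** Six months for women conflicts with the Appendix 1 opening. For men, six months is longer than the four months in criterion 6B, so that difference errs on the safe side.

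The number of women of childbearing potential is not given, so the number who could be affected cannot be estimated.

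**The case against.** The strongest reply is that a reader is unlikely to rely on Section 8.5.3 or 4.5 alone. Criterion 6A says seven months and names cross-over and re-treatment. Section 4.5, in the same paragraph, requires adherence to the exclusion criteria and Appendix 1. The pregnancy-test sentences of Section 8.5.3 cite Section 5 and Appendix 1, and Section 7 ties the consent discussion to Section 5. Consent-form changes went to all enrolling sites, and Amendment 2.0 required a revised consent. Section 4.5 is a risk-benefit rationale, not a procedure. Seven months is itself a precaution beyond the calculated period.

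Most of this stands, and it is why the point is minor. It does not remove the conflict. Appendix 1, to which readers are sent, itself contains both 6 and 7. The re-treatment eligibility list in Section 5.2.2 does not repeat criterion 6A, and Table 8-3 leaves the inclusion and exclusion check out of the re-treatment procedures. Six months is also below the calculated period, not only below the precautionary one. The clause that takes the longer period does not help when treatment ends early.

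A reader might also infer that Section 4.5 contradicts Section 7 on fetal risk. Section 4.5 says that "taking the study treatment may involve unknown risks to the fetus if pregnancy were to occur during the study"; Section 7 says that "taking Lutathera can cause fetal harm when administered to a pregnant woman". The documents do not support a contradiction. The first concerns study treatment in general and addresses women and men; the second concerns Lutathera and addresses women. Both can be true.

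**Conclusion.** The inconsistency is real and minor. Section 8.5.3 is wrong as written: it is up to 30.4 days short of the sponsor's rule and up to 10.2 days short of the calculated period. The shortfall arises only for a woman whose treatment period ends before the longer date, and only if the reader does not follow criterion 6A or the Appendix 1 opening. The week figures assume the fourth dose at Week 24. Section 4.5 and the later Appendix 1 sentence need the same correction. The statistical analysis is unaffected.

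Three stronger readings are not supported:

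- **That women were given the wrong period.** The consent form was not available and most of Appendix 5 was removed from the text reviewed. The documents say only that a revised consent was required.
- **That the later Appendix 1 sentence gives a shorter period than the Appendix 1 opening.** That depends on whether stopping study drug includes octreotide, which Lutathera-arm patients continue after the fourth dose. On that reading the sentence may run longer.
- **That the six months of Germany-only pregnancy testing in Section 8.5.3 is part of the error.** A testing period need not equal a contraception period.

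**What to change.** Make three edits:

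1. **Section 8.5.3:** change six to seven months after the last Lutathera treatment.
2. **Section 4.5:** state seven months for women and four months for men after the last Lutathera treatment.
3. **Later Appendix 1 sentence:** change only 6 to 7 months and keep study drug discontinuation as the start. Moving the start to the last Lutathera dose would create a new conflict with criterion 6A, leave control-arm women who never receive Lutathera without an end point in that sentence, and could shorten the period for women continuing octreotide.

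Optionally, add to Section 4.5 that Lutathera can cause fetal harm. The existing sentence should stay, because replacing it would drop men and study treatment in general. The sponsor should also confirm that the consent form and Appendix 5 say seven months.

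Section 14.1 requires a written amendment approved by the sponsor, health authorities where required, and the IRB/IEC. The edits are best bundled with the next amendment, with a clarification letter to sites meanwhile. No data or analysis changes.

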8.5.4 Cardiac Ejection Fraction

Patients with uncontrolled congestive heart failure (NYHA II, III, IV) are not eligible according to exclusion criteria.

Patients with history of congestive heart failure who do not violate this exclusion criterion will undergo an evaluation of their cardiac ejection fraction prior to randomization via echocardiography. The results from an earlier assessment (not exceeding 30 days prior to randomization) may substitute the evaluation at the discretion of the Investigator, if no clinical worsening is noted. The patient's measured cardiac ejection fraction in these patients must be $\geq 40\%$ before randomization.

8.5.5 ECG

Standard 12-lead ECGs will be performed using the device provided by the Sponsor (central assessment). ECGs will be recorded at baseline, after each Lutathera treatment procedure (following the completion of the amino acids infusion), at the end of study treatment and at the end of study follow up phase to measure the different ECG intervals (RR, PR, QRS, and a more extended QT evaluation according to ICH E14). ECGs will be taken also in the 60 mg octreotide long-acting arm at same time points (before the octreotide long-acting injection). See ECG Manual for further details and visits schedule in Table 8-3, and Table 8-4).

An ECG in triplicate (at least 5 minutes apart) will be taken supine, after 10 minutes rest, and not immediately after a meal. The parameters will be measured as a mean value of minimally 3 beats. The preferred sequence of cardiovascular data collection during study visits is ECG collection first, followed by vital signs, and blood sampling.

Additional, unscheduled, safety ECGs may be repeated at the discretion of the investigator at any time during the study as clinically indicated. Unscheduled ECGs with clinically significant findings should be collected in triplicate. Local cardiologist ECG assessments may also be performed at any time during the study at the discretion of the investigator.

All ECGs, including unscheduled triplicate safety ECGs with clinically relevant findings, collected during the study should be transmitted to the central core ECG laboratory for review.

The Investigator/local cardiologist will note in the source documents (and in the eCRF) whether the ECG is normal or abnormal, as well as the clinical relevance of abnormal ECGs results based on their own review of the ECG tracing. Relevant abnormalities at baseline will be recorded in the medical history page, while changes during the study will be recorded on the Adverse Event page of the eCRF.

The original ECGs on non-heat-sensitive paper or a certified copy on non-heat sensitive paper, appropriately signed, must be collected and archived at the study site. Any identifier details must be redacted e.g. subject initials, date of birth. Each ECG tracing should be labeled with the study number, subject initials (where regulations permit), subject number, date, and kept in the source documents at the study site.

The results of the centrally assessed ECGs are automatically transferred into the clinical database.

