Height	Х																												the new consent and		
Weight	Х	Х	X	(X	(X X	X	Х	Х	Х	Х	Х	Х		Х			Х			>	<			Х		Х	Х	have SRI imaging		Х
Vital Signs	Х	Х	(X	x		Х			Х			Х			Х			>	<			Х		Х	х	documenting tumor		Х
Karnofsky Performance	х	Х				>	×					Х			Х			Х			>	<			Х		Х	х	treatment. SSA administration at	х	х
Cardiac Ejection Fraction ²	х																												investigator judgment.		
Randomization and Lutathera order (after all elig bility criteria are verified) ³	X																														
Blood chemistry	Х		Х	(X	(x >	x	Х	Х	Х	Х	Х	Х		Х			Х			>	<			Х		Х	Х	1	Х	Х
Hematology	Х		Х	(X	(X)	x	Х	Х	Х	Х	Х	Х		Х			Х			>	<			Х		Х	Х]	Х	Х

Assessment Schedule Lutathera Arm – cont.

Confidential

Visit Name	Screen ng	i Tro	eatr	mer	nt																					Further Visits	EOT o termin	r early ation	Optional re- treatment	3 years follow-	EOS or early
																										after 72 weeks ¹			(2-4 Lutathera cycles)	up	FUP termin ation
Weeks	-2 - 0	0	4	6	8	1:	2 14	16	5 2	0 23	2 2	4 28	3 32	2 30	ô 4	0 4	14	48	52	56	60	6	46	58	72	Every 4 weeks	Every 12 weeks	Within 4 weeks from last treatment		Every 6 months	Last FUP visit
Treatment		+			-			1	•			∎ ↓	•	+	+	t	+	+	+	+		ŀ	t	+	+	+	+		2-4x ♣↓		
Pregnancy Test	Х		X ⁴		X	X	(4	X	X	(4)	< X	4 X	4 X	(4 X	(4)	X ⁴	X4	X ⁴									X4	Complete all		
Serum CgA⁵	Х)	Х					Х			X			Х			Х	(Х		Х	Х	assessments and		Х
SRI (eg SomaKit or Netspot or OctreoScan) ⁶	Х																												procedures in Table 8-3 from week -2 (except demography, INC/EXC criteria		
SPECT/CT and WBPI ⁷		X7			X	7		Х	7		X	7																	cancer diagnosis and grading, medical		
CT/MRI (central re- assessment during treatment phase)	х							>	×			×			x			Х			Х	(Х		х	X ⁹	history, randomization, QoL) until disease	х	X ¹¹
ECG (central re- assessment; Sponsor device) [at the end of amino acids infusion during treatment]	X	x			>	K		>	K			×																X	which EoT visit is done and patient proceeds into follow up. Patients must sign the new consent and		х
Adverse Events ⁸	Х	Х	X	$\langle \rangle$	$\langle \rangle$	<)	x >	$\langle \rangle$	<]	X X	X	x)	$\langle \rangle$	(X	Х	Х	Х	Х	Х	X	()	Х	Х	Х	Х	Х	Х	have SRI imaging	Х	Х
Prior/Concomitant Medications/New Anticancer therapy	x	X	X		< >	()	x >	()	x :	X X	X	x >	()	()	X	x	Х	Х	Х	Х	X		x	х	Х	Х	Х	X	documenting tumor uptake before re- treatment. SSA administration at	X ¹²	X ¹²
Lutathera/Amino Acid/Anti-emetics		Х			>	<		>	<			x																	investigator judgment ¹⁰ .		

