Cancer diagnosis and grading	Х																							grading, medica history, randomization)		
Prior therapy for carcinoid tumor	х																							to Week 24 (last Lutathera dose) after which EoT visit is done and		
Medical history	Х																							patient		
Physical Exam	Х	Х			Х			Х			Х			Х			Х			Х		Х	Х	proceeds into		Х
Height	Х																							Patients must		
Weight	Х	Х	Х	Х	Х	Х	Х	Х	Х		Х			Х			Х			Х		Х	х	sign the new		Х
Vital Signs	Х	Х		Х	Х	Х		Х			Х			Х			Х			Х		Х	Х	consent before		Х
Karnofsky Performance	х	х			х			Х			Х			Х			Х			Х		Х	X	have SRI imaging	Х	х
Cardiac Ejection Fraction ³	x																							documenting tumor uptake. All protocol		
Randomization (after all eligibility criteria are verified) ⁴	x																							inclusion/exclusi on criteria must be re-verified.		
Blood chemistry	Х		х	х	х	х	х	х	х		х			х			х			х		x	x		х	х
Hematology	Х		Х	X	Х	Х	Х	Х	Х	1	Х		1	Х			Х		1	X		Х	х		х	х

Assessment Schedule Octreotide Long-Acting 60 mg Arm – cont.

Confidential

Visit Name	Scree ning	Tre	eatmo	ent																	Furthe after 72	r Visits 2 weeks¹	EOT or early terminatio n	Optional Treatment Extension (4 Lutathera	3 years follow- up	EOS or early FUP termin ation
Weeks	-2 - 0	0	4	8	12	16	20	24	28	32	36	40	44	48	52	56	60	64	68	72	Every 4 weeks	Every 12 weeks	Within 4 weeks from last treatment	cycles) ²	Every 6 months	Last FUP visit
Treatment		+	+	+	+	+	+	+	+	+	+	+	+	+	+	+	+	+	+	+	+	+		4x ♥↓		
Pregnancy Test	Х																						X ⁵	Complete all		
Serum CgA	Х				Х			Х			Х			Х			Х			Х		Х	Х	assessments in		Х
SRI (SomaKit or Netspot or OctreoScan) ⁷	х																							week -2 (except demography, cancer diagnosis		
CT/MRI (central re-assessment during treatment phase)	x					X		X			Х			X			X			x		X	X ¹⁰	and grading, medical history, randomization) to Week 24 (last Lutathera dose),	x	X ¹¹
ECG (central re- assessment; Sponsor device)	Х	Х		X		х		х															X	after which EoT visit is done and patient proceeds		X
PK (central assessment) ⁸			х		х	х		х																Patients must		
Adverse Events9	Х	Х	Х	Х	Х	Х	Х	Х	Х	Х	Х	Х	Х	Х	Х	Х	Х	Х	Х	Х	Х	Х	Х	consent before	Х	Х
Prior/Concomitant Medications/New Anticancer therapy	X	x	x	X	×	×	×	X	×	X	×	×	Х	x	x	×	X	x	×	x	X	X	x	cross-over and have SRI imaging documenting tumor uptake. All protocol inclusion/exclusio n criteria must be re-verified.	X ¹²	X ¹²

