2.1.1.8 Baseline

For efficacy evaluations, the last non-missing assessment, including unscheduled assessments on or before the date of randomization is taken as “baseline” value or “baseline” assessment. In the context of baseline definition, the efficacy evaluations also include PRO.

For safety evaluations (e.g., laboratory assessments, ECGs, and vital signs), the last available assessment, including unscheduled assessments, on or before the start of study treatment as described in [Section 2.1.1.4](#) will be used as the “baseline” assessment. Assessments specified to be collected post-dose on the 1st date of treatment are not considered as baseline values.

If participants have no value as defined above, the baseline results will be considered missing.

Since study treatment in the randomized treatment phase can still potentially contribute to the safety profile in the cross-over and re-treatment phase, therefore, for cross-over and re-treatment analyses, baseline for safety analysis is the same as defined above, i.e., last available assessment on or before the start of study treatment.

For efficacy evaluations of the cross-over and re-treatment period, the last available assessment on or before first cross over treatment/re-treatment with Lutathera® is regarded as “baseline” for the assessments.

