2.8.4 Other safety data

2.8.4.1 ECG data

ECG data will be summarized by presenting summary statistics of the raw data and change from baseline by treatment group and time point. Notable ECG values will be summarized for the randomized treatment period. All ECG data will be included in listings, and those beyond the randomized treatment period will be flagged by study period.

Notable elevations of ECG summarize the number of participants meeting or exceeding predefined limits in terms of absolute QT/QTc interval data/PR/RR/QRS or changes from baseline as defined in [Table 2.8-2](#), and notable elevations of ECG includes only newly occurring ECG abnormality. A newly occurring ECG abnormality is defined as an abnormal post-baseline ECG finding that is not present at baseline. The percentage of participants having notable ECG interval values is based on the number of participants at risk for the change with a value at baseline and post-baseline.

Table 2.8-2 Clinically notable ECG values

ECG parameter (unit)	Clinically notable criteria
QT, QTcF (msec)	New > 450 and \leq 480 New > 480 and \leq 500 New > 500 Increase from Baseline > 30 and \leq 60 Increase from Baseline > 60
PR duration (msec)	Increase > 25% from baseline and to PR duration > 200 New > 200
QRS duration (msec)	Increase > 25% from baseline and to QRS duration > 120 New > 120
Heart rate (beats/min)	<50 and decrease from baseline of > 25% > 100 and increase from baseline of > 25%

All ECG data will also be listed by treatment group, participant, and visit. Abnormalities will be flagged.

An ECG in triplicate (at least 5 minutes apart) is recorded with the patient supine, after 5-minute rest, and not immediately after a meal. The parameters will be measured as a mean value of minimally 3 beats; the mean of each parameter will be used for statistical analysis. If an ECG is conducted, but data is not available in triplicate, the average of the ECG parameters at that assessment by (un)scheduled visit should be used in the analysis.

Frequency tabulations for the ECG interpretation (Normal / Abnormal, not clinically significant / Abnormal, clinically significant) will be presented.

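### The Week 0 ECG counts as post-baseline on Lutathera but as baseline on control, so the count of newly notable ECGs gives Lutathera one extra scheduled chance (5 vs 4)

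*Protocol*

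**What the plan says.** **Timing.** For the Lutathera arm, Protocol 8.5.5 states: "ECGs will be recorded at baseline, after each Lutathera treatment procedure (following the completion of the amino acids infusion"). For control: "ECGs will be taken also in the 60 mg octreotide long-acting arm at same time points (before the octreotide long-acting injection"). Table 8-3 repeats the post-infusion timing ("at the end of amino acids infusion during treatment"). The ECG rows of Tables 8-3 and 8-4 mark the same visits in both arms: screening, Weeks 0, 8, 16 and 24, EOT and end of study.

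**Baseline.** SAP 2.1.1.8 defines the safety baseline as "the last available assessment, including unscheduled assessments, on or before the start of study treatment". It adds: "Assessments specified to be collected post-dose on the 1st date of treatment are not considered as baseline values".

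**Analysis.** SAP 2.8.4.1 states: "Notable ECG values will be summarized for the randomized treatment period". It counts only new findings: "A newly occurring ECG abnormality is defined as an abnormal post-baseline ECG finding that is not present at baseline". The denominator is patients at risk who have both a baseline and a post-baseline value. SAP 2.1.1.10 starts the randomized treatment period on the date of first administration and ends it 30 days after the last one, or the day before cross-over or re-treatment if that is earlier.

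**The concern.** The two arms have the same ECG visits, but one of those visits changes role between them. An abnormality first seen at Week 0 counts as new on Lutathera. On control the same finding becomes the baseline and can no longer be new.

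The baselines also differ in age. On control the baseline ECG is taken on the day of first injection. On Lutathera it dates from screening, and Protocol 3.1 allows about 12 days after randomization to produce and ship the first dose.

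What is at stake is how the between-arm ECG display is read. Protocol 8.5.5 asks for an extended QT evaluation, and Protocol 10.1.5 makes cardiovascular and electrolyte disorders an adverse event category of special interest. A built-in excess on Lutathera could be taken for a drug or infusion effect, or could blur a real one.

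**Working it through.** The plan states no expected number of post-baseline ECGs and no expected rate of notable values, so there is no figure of its own to reproduce.

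**Step 1: role of each scheduled ECG** (Tables 8-3 and 8-4 read with SAP 2.1.1.8 and 2.1.1.10).

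| Visit | Lutathera | Control |
|---|---|---|
| Screening | baseline | replaced by Week 0 |
| Week 0 | post-infusion: post-baseline | pre-injection: baseline |
| Weeks 8, 16, 24 | post-baseline | post-baseline |
| EOT | post-baseline | post-baseline |
| Scheduled post-baseline ECGs | 5 | 4 |

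EOT is due within 4 weeks (28 days) of last treatment, so it normally falls inside the 30-day limit in both arms. The gap of one persists for patients who stop early: after 1, 2, 3 or 4 ECG treatment visits plus EOT, the counts are 2 vs 1, 3 vs 2, 4 vs 3 and 5 vs 4.

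**Step 2: upper bound, independent ECGs.** Let p be the chance of a notable value at any one ECG, equal in both arms (no drug effect). The chance of at least one in k ECGs is 1 − (1 − p)^k, with k = 5 for Lutathera and 4 for control. At p = 5%: 1 − 0.95^5 = 22.6% and 1 − 0.95^4 = 18.5%.

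**Step 3: correlated ECGs.** Repeat ECGs in one patient are correlated, and patients already abnormal at baseline cannot be new. A beta-binomial model with within-patient correlation r, conditional on a baseline that is not notable, allows for both. Set a = p(1 − r)/r and b = (1 − p)(1 − r)/r. The chance of no notable value in k ECGs is the product over i = 1 to k of (b + i)/(a + b + i).

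At p = 5% and r = 0.5, a = 0.05 and b = 0.95:
- k = 4: (1.95/2)(2.95/3)(3.95/4)(4.95/5) = 0.937, so 6.3%.
- k = 5: multiply by 5.95/6 to get 0.929, so 7.1%.

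**Results, Lutathera vs control** (p and r are assumptions):

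| p | independent | ratio | r = 0.3 | r = 0.5 |
|---|---|---|---|---|
| 0.5% | 2.5% vs 2.0% | 1.25 | 1.2% vs 1.0% | 0.7% vs 0.6% |
| 2% | 9.6% vs 7.8% | 1.24 | 4.6% vs 4.0% | 2.9% vs 2.5% |
| 5% | 22.6% vs 18.5% | 1.22 | 11.3% vs 9.8% | 7.1% vs 6.3% |
| 10% | 41.0% vs 34.4% | 1.19 | 21.5% vs 19.0% | 13.7% vs 12.3% |

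At p = 5%, with the planned 148 Lutathera patients, the artificial excess is about 6 patients under independence (148 × 4.07%), about 2 at r = 0.3 (148 × 1.43%) and about 1 at r = 0.5 (148 × 0.78%).

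With four matched visits in each arm the formula is the same on both sides, and the built-in difference is zero.

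**The case against.** The strongest reply is that the effect is small and sits in a low-stakes table. SAP 2.8.4.1 plans summary statistics, counts, percentages and listings, with no between-arm test. The error runs against the investigational product, so it is conservative for safety. Intervals such as QTcF, PR and QRS can be expected to be fairly stable within a patient, which pulls the excess towards the correlated columns. Actual ECG counts will differ anyway through early discontinuation and the unscheduled ECGs that Protocol 8.5.5 allows. The ECG Manual it cites was not available for this check. All of this stands and limits the size of the point. It does not remove the asymmetry, for which neither document makes an adjustment.

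It is also fair to say that the post-infusion timing may be deliberate, to capture acute effects of the infusion. The point does not question when ECGs are collected, only how the arms are compared.

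Two stronger readings are tempting but unsupported:
- A reader might infer that every on-treatment ECG is post-dose in one arm and a pre-dose trough in the other. The EOT ECG is not tied to an infusion or injection in either arm, and the control Week 0 ECG precedes any study dose.
- A reader might object that control change from baseline at Week 0 is zero by construction. That is no defect: a visit that serves as baseline has no change to report, and the SAP does not say that one will be displayed.

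**Conclusion.** The point holds as a limited one. Under the current text the Week 0 ECG is post-baseline on Lutathera and baseline on control, giving 5 vs 4 scheduled chances of a newly notable value. With no drug effect the summary tends to show a small excess on Lutathera. The ratio is at most about 1.19 to 1.25 for p from 0.5% to 10% under independence, and smaller with within-patient correlation (about 1.12 to 1.13 at correlation 0.5).

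These sizes rest on an assumed p that is equal across arms and visits, an assumed correlation, and complete scheduled ECGs. The difference in baseline age is not in the model and is not quantified. Only the descriptive ECG safety summary is affected; the primary and key secondary analyses are not. This is a cheap improvement, not a threat to the trial's conclusions.

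**What to change.** In SAP 2.8.4.1:
- Define the ECG baseline as the screening-visit ECG in both arms. Naming the visit matters: a rule based on the randomization date could still pick the Week 0 ECG for a control patient randomized and injected on the same day.
- Base the between-arm comparison of newly notable values on the matched visits: Weeks 8, 16, 24 and EOT.
- Keep the all-visit table, with the Lutathera Week 0 post-infusion ECG as its own row, so that the first-exposure signal stays in the main safety display.
- Footnote that ECGs at Weeks 0, 8, 16 and 24 are post-infusion on Lutathera and pre-injection on control.

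The cost is SAP wording and reprogramming of one derived baseline and the tables that use it. No new ECGs are needed. The downside is that the control Week 0 ECG, which is closer to first dose, is no longer the baseline. The post-dose versus pre-dose difference at Weeks 8 to 24 also remains, which is why the footnote is needed. Counting Week 0 in both arms against a screening baseline (5 vs 5) would also equalize the counts, but it would count a control ECG taken before any study drug as post-baseline.
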